## 7.4 PRIMARY ENDPOINT(S)

### 7.4.1 Primary analysis of the primary endpoint(s)

The primary endpoint is the change from baseline to Week 10 in ZAN-BPD total score. Baseline refers to the measurement recorded at randomization (Visit 2), if data at Visit 2 is missing, then data from Visit 1 will be considered baseline.

Despite the COVID-19 pandemic, the collection of complete data at all visits is our goal. Therefore, to avoid missing data due to a subject's potential inability to attend their in-person clinical visit, a virtual assessment via videoconferencing will be available to ascertain the ZAN-BPD. For the primary analysis of the primary endpoint, we assume no discernible difference between the in-person and virtual collection of the ZAN-BPD. Hence, all data while subjects are on treatment, whether in-person or virtual, will be used in the evaluation of the primary analysis of the primary endpoint.

The primary analysis of the primary endpoint will use a hypothetical estimand. The hypothetical approach focuses on the treatment effect assuming all subjects complied with the CTP and remained on the assigned trial medication, i.e., study drug is taken as directed. Hence, the hypothetical estimand evaluates the treatment effect if intercurrent events do not occur. Therefore, this analysis will include all data collected while on treatment which is defined as the time from the date of the first dose of trial medication until the date of the last dose of trial medication plus 7 days. Any data collected after a patient discontinues trial drug, regardless of reason, will be censored and will not be included in the primary analysis. Therefore, the primary analysis of the primary endpoint will be evaluated under the hypothetical estimand regardless of the potential influence of COVID-19.

The Multiple Comparison Procedures and Modelling (MCPMod) approach (8, 9) is implemented in two main stages: (1) **trial design stage**; (2) **trial analysis stage**. The procedures for the trial design stage, including the selection of candidate models covering a suitable range of dose-response shapes and sample size and power calculations are provided in the CTP Section 7.2.2 and 7.5. The procedures for the trial analysis stage are specified below. FAS is used for the primary analysis of the primary efficacy endpoint.

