## 4.2.2 Restrictions

### 4.2.2.1 Restrictions regarding concomitant treatment

Following medications are prohibited during the treatment period:

- All psychotropic medications except short term usage of protocol stipulated benzodiazepines and non-benzodiazepine hypnotics (described below)
- 
- Use of alternative or traditional medicines (e.g. Chinese traditional medicine, herbal medication, St. John's Wort, Ayurveda medications, etc.).

Participants on statins should be monitored for statin related toxicity including signs of myopathy, weakness, muscle pain, etc. along with clinical lab results. If statins are concomitantly used during the trial, the highest dose should not be taken together with the study drug. If participant in this trial is on the highest recommended statin dose, the investigator should consider changing the statin dose to the next lower dose recommended for the respective statin, if appropriate.

Concomitant use of benzodiazepines and non-benzodiazepine hypnotics are allowed during study for up to 7 days at a dose equivalent to  $\leq 1.0$  mg of lorazepam per day, for the management of AEs (e.g. anxiety and/or insomnia). Such drugs should be stopped after the AE is resolved, at the discretion of the investigator. If a longer duration of treatment is needed, re-evaluation of the need for treatment by the investigator is required every 7 days per treatment cycle. Refer to ISF for dose equivalency information.

In case of AEs, any treatment deemed necessary per the clinical judgment of investigator for the management of AEs considering patient safety is allowed.

For further guidance, investigators should refer to the current IB or contact the sponsor.

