## 7.2.2 Primary endpoint analyses

### 7.2.2.1 Primary analyses

As defined in section [2.1.2](#), the primary endpoint is the change from baseline to Week 10 in ZAN-BPD total score. Baseline refers to the measurement recorded at randomization (Visit 2), if data at Visit 2 is missing, then data from Visit 1 will be considered baseline.

The primary estimand of interest is the treatment effect assuming all subjects remained adherent to the assigned trial medication and the study protocol using a hypothetical approach, i.e. study drug is taken as directed. The primary analysis of the primary endpoint will include all data collected while on treatment which is defined as the time from the date of the first dose of trial medication until the date of the last dose of trial medication plus 7 days (3 times the estimated elimination half-life). Any data collected after a patient discontinues trial drug, regardless of reason, will be censored and will not be included in the primary analysis.

The analyses for PoC and dose-finding will be performed using multiple comparison and modelling techniques (MCPMod). MCPMod is used to evaluate several possible dose response models (patterns) and to identify the best-fitting model or subset of models based on the BI 1358894 and placebo treatment groups while keeping full control of the type I error at 10%, one-sided. The primary endpoint will be analyzed using a mixed model repeated measures model (MMRM) which is valid under the missing at random (MAR) assumption. Under the MMRM model, there's no explicit imputation of missing data, rather, the future statistical behavior of those participants who drop out given their past measurements is assumed to be the same as those who remain with the same history.

In particular, between-treatment differences in the change in ZAN-BPD total score at Week 10 (from baseline) will be evaluated using a MMRM adjusted for treatment arm, clinical visit and baseline ZAN-BPD total score. In addition, participants will be included in the model as a random effect. Additional covariates (such as stable concomitant psychotherapy use (yes/no) and sex) or factors identified prior to database lock may be included in the MMRM model as applicable.

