### **3. INTRODUCTION**

As per International Conference on Harmonisation (ICH) E9 (1), the purpose of this document is to provide a more technical and detailed elaboration of the principal features of the analysis described in the CTP, and to include detailed procedures for executing the statistical analysis of the primary and secondary variables and other data.

This Trial Statistical Analysis Plan (TSAP) assumes familiarity with the Clinical Trial Protocol (CTP), including Protocol Amendments. In particular, the TSAP is based on the planned analysis specification as written in CTP [Section 7](#) “Statistical Methods and Determination of Sample Size”. Therefore, TSAP readers may consult the CTP for more background information on the study, e.g., on study objectives, study design and population, treatments, definition of measurements and variables, planning of sample size, randomization.

R Version 3.3.2 with “DoseFinding” package (2) will be used for analyses based on Multiple Comparison Procedures and Modelling (MCPMod) and SAS® Version 9.4 will be used for all other analyses.

The main analyses of this TSAP will be conducted under the estimand concept. To quote ICH E9 R1, “An estimand is a precise description of the treatment effect reflecting the clinical question posed by a given clinical trial objective. It summarizes at a population level what the outcomes would be in the same patients under different treatment conditions being compared.” So, an estimand is a way for the clinical trial protocol to address how intercurrent events will be handled. And according to ICH E9 R1, intercurrent events are events occurring after treatment initiation that affect either the interpretation or the existence of the measurements associated with the clinical question of interest. Or in other words, intercurrent events are occurrences after randomization that involve a change in treatment regimen.

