### **6.3 SUBJECT SETS ANALYSED**

The following analysis sets are defined for this trial:

- Screened Set (SS): consists of all subjects who signed informed consent.
- Treated Set (TS): consists of all subjects that have been randomized and that received at least one administration of study drug. The TS will be the main analysis set for the evaluation of safety. Subjects are analysed according to the actual received treatment.
- Full analysis set (FAS): consists of all subjects in TS that have a baseline and at least one evaluable post-baseline measurement for the primary endpoint. This is the main analysis set for the evaluation of efficacy data.
- Per protocol set (PPS): This is a subset of FAS, for subjects with adequate protocol compliance. It consists of all subjects in FAS without any important protocol deviations that impact efficacy assessments.
- Adherent set (AS): consists of all subjects in FAS that are at least 60% overall AiCure adherent to study medication. See [Section 7.3.2](#) for further information.

- 

Table 6.3: 1 Subjects' sets analyzed

| Class of endpoint  | Subject set |    |     |     |   |    |
|--|-------------|----|-----|-----|---|----|
|  | TS          | SS | FAS | PPS | █ | AS |
| Primary and secondary endpoints, compliance                  |             |    | X   | X*  |   |    |
| Further endpoints (except PK)                                |             |    | X   |     |   |    |
| Disposition  |             | X  |     |     |   |    |
| █  |             |    |     |     | █ |    |
| Safety variables and iPDs                                    | X           |    |     |     |   |    |
| Demographics, baseline variables, exposure                   |             |    | X   | (X) |   |    |
| Primary endpoint adjusted for overall study AiCure adherence |             |    |     |     |   | X  |

\* If the percentage of subjects in FAS with iPD that lead to the exclusion from the PPS is > 10%, then sensitivity analysis of the primary and secondary efficacy endpoints using PPS may be conducted.

(X) An additional PPS presentation of the demographic/baseline endpoints may be provided in the End of Text (EoT) section, if there are a non-negligible number of subjects that were treated, but without any post randomization data for the primary endpoint.

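### The primary estimand is labelled purely hypothetical, but only trial-drug discontinuation has a data rule; on-drug scores after a new psychotropic or a psychotherapy change stay in, so the strategy is in fact mixed.

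*SAP*

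**What the plan says.** **The target.** Protocol 7.2.2.1 sets out the effect "assuming all subjects remained adherent to the assigned trial medication and the study protocol using a hypothetical approach", and Protocol 7.3 repeats it. SAP 7.4.1 words it as "The hypothetical approach focuses on the treatment effect assuming all subjects complied with the CTP and remained on the assigned trial medication", with the gloss that drug is taken as directed, and then widens it again: "the hypothetical estimand evaluates the treatment effect if intercurrent events do not occur". SAP section 3 puts the idea of an intercurrent event in plain terms: "intercurrent events are occurrences after randomization that involve a change in treatment regimen".

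**The data rule.** SAP 7.4.1 states that "this analysis will include all data collected while on treatment which is defined as the time from the date of the first dose" until seven days after the last dose. Data after trial-drug discontinuation are censored. Protocol 7.2.2.1 and 7.3 also tie censoring to discontinuation.

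**Other therapy during treatment.** Protocol 4.2.2.1 prohibits psychotropics, apart from limited use of benzodiazepines and non-benzodiazepine hypnotics. It then adds: "In case of AEs, any treatment deemed necessary per the clinical judgment of investigator for the management of AEs considering patient safety is allowed". Under Protocol 6.2.1 (Medical History), significant psychotherapy changes are recorded at clinic visits. No visible analysis rule is attached to either.

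**Nearest safeguards.** If more than 10% of the FAS would be excluded from the per-protocol set, "then sensitivity analysis of the primary and secondary efficacy endpoints using PPS may be conducted" (SAP 6.3, repeated in 7.4.2.1). SAP 6.2 provides for review of deviations and discrepant values before database lock.

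**The concern.** An estimand that assumes full compliance and no intercurrent events needs a rule for each such event that can occur while the patient remains on drug. Here only one event has a rule.

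The others are foreseeable. Protocol 1.1 describes off-label drug treatment as common in this disorder, patients enter off most psychotropics, and the adverse-event clause allows new treatment. Starting a prohibited psychotropic is not in itself a listed reason to stop trial drug (Protocol 3.3.4.1), so it does not automatically trigger censoring.

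Such therapy can act on the symptoms that ZAN-BPD measures. At stake are what the Week 10 means fed into MCPMod represent and, through them, the target-dose estimate. A reader of the trial report would take the result as a purely hypothetical effect when it is not.

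**Working it through.** **Step 1. Event against rule, from the visible text.**

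| Event while in the trial | Within the stated target? | Later scores in primary MMRM | Later scores in treatment-policy analysis |
|---|---|---|---|
| Trial drug stopped | Yes | Censored (after the 7-day window) | Kept |
| Prohibited psychotropic started, drug continued | Yes: departs from the protocol and changes treatment | Kept | Kept |
| Psychotropic given under the adverse-event clause, drug continued | Yes, as an intercurrent event; the protocol allows it | Kept | Kept |
| Short-term benzodiazepine or hypnotic within the stated limits | Can be, as an intercurrent event; the protocol allows it | Kept | Kept |
| Significant psychotherapy change, drug continued | Yes, as an intercurrent event; no visible text prohibits it | Kept | Kept |

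Only the first row differs between the two analyses. SAP 7.4.2.2 presents the treatment-policy analysis as using data after discontinuation or other intercurrent events. For the last four rows the primary analysis already uses those data, so comparing the two cannot show what these events do.

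**Step 2. Does another provision close the gap?**

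- Per-protocol analysis: optional, conditional on the 10% threshold, and removes whole patients rather than the affected scores.
- Pre-lock review (SAP 6.2): can decide on single values, but case by case. It is not a pre-stated estimand rule.
- Psychotherapy covariate (SAP 7.4.2.1): stable use yes or no, not change during treatment, and only in a sensitivity model.
- AiCure subgroups (SAP 7.4.2.3): concern tablet-taking and are exploratory.

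None of these changes the primary rule.

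**Step 3. Size.** The plan's reference effect is a difference of 3.0 with SD 9.5 (Protocol 7.5): 3.0 / 9.5 = 0.316, the stated 0.32. The documents give neither the share of patients affected nor the extra improvement, so what follows is assumption only.

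Observed difference = 3.0 − (placebo share − active share) × extra improvement in affected patients

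| Placebo share | Active share | Extra improvement 3 points | Extra improvement 5 points |
|---|---|---|---|
| 5% | 0% | 3.0 − 0.15 = 2.85 | 3.0 − 0.25 = 2.75 |
| 20% | 0% | 3.0 − 0.60 = 2.40 | 3.0 − 1.00 = 2.00 |
| 20% | 10% | 3.0 − 0.30 = 2.70 | 3.0 − 0.50 = 2.50 |
| 20% | 20% | 3.00 | 3.00 |
| 0% | 10% | 3.0 + 0.30 = 3.30 | 3.0 + 0.50 = 3.50 |

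The 5-point column is an extreme, since it exceeds the maximum effect assumed for the trial drug. With the same share in every active arm, all active-placebo differences shift equally. If the share varied by dose, the shape of the curve would change too.

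**The case against.** **The target is really drug adherence.** The gloss in SAP 7.4.1 and Protocol 7.2.2.1 points to taking drug as directed, and Protocol 2.1.1 describes an on-treatment characterization. Section 3 of the SAP could also be read as meaning a change in the trial regimen only. This has weight: censoring at discontinuation serves most of that narrower target. It does not settle the matter. The sentence after the gloss returns to intercurrent events without limit, section 3 also cites the wider ICH definition (events that affect interpretation of the measurements), and SAP 7.4.2.2 expects other intercurrent events. Even the narrow target is not fully met, because on-drug scores after missed tablets also stay in.

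**Much of this therapy is not a breach.** This stands. Treatment under the adverse-event clause, and benzodiazepines or hypnotics within their limits, comply with the protocol. Stable psychotherapy is an entry condition with stated intent. A reader might infer that all these patients violated the protocol; the documents do not support that. They have intercurrent events without a stated strategy.

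**Review before lock may deal with it.** It may, value by value, and the deviation specifications are not visible. A reader might infer that affected scores are certain to remain untouched, or that no other data are ever removed. Neither can be claimed, particularly since parts of Protocol 7.2 and SAP 6.4 and 10 are not shown. The visible primary-analysis text is nevertheless consistent in all three places.

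**Removing scores has a price.** Patients given new therapy may be worsening, so setting their scores to missing leans more on missing at random, on top of the 20% dropout assumed. This stands, and is why restating the estimand is an acceptable alternative.

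**Conclusion.** The point holds as a mismatch between the estimand and its data rule. For new psychotropics and psychotherapy changes while on drug, the visible plan applies a treatment-policy strategy under a hypothetical label. This follows from the text and needs no assumption beyond reading intercurrent events as the SAP defines them.

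The numerical consequence is not known. A reader might infer that the primary result is biased in a particular direction, or that power falls by a definite amount. The documents give no event rates, so neither follows. On the assumed values above, a 3.0-point difference could appear as anything from 2.0 to 3.5, and balanced use leaves it at 3.0. The sample size is unaffected, since the point concerns which scores enter the model.

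**What to change.** Before unblinding, add to SAP 7.4.1 a list of intercurrent events, each with its strategy:

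1. trial-drug discontinuation;
2. psychotropics prohibited under Protocol 4.2.2.1;
3. psychotropics given under the adverse-event clause;
4. short-term benzodiazepines or hypnotics;
5. significant psychotherapy change.

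For each event handled hypothetically, set ZAN-BPD scores from the event date onward to missing in the primary MMRM, and keep them in the treatment-policy analyses. Start dates of concomitant therapy are among the source data (Protocol 8.3.1). No event date is visible for psychotherapy, so use the first clinic visit at which the change is recorded.

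Otherwise, restate the primary estimand as hypothetical for discontinuation and treatment policy for concomitant therapy.

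The first option costs SAP text and a derivation from data already collected. A few ratings leave the primary analysis, and it relies slightly more on missing at random. The second costs wording only. Neither changes a clinical rule.

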#### MMRM analysis

The change from baseline in ZAN-BPD at Week 10 for each dose group as well as the corresponding variance-covariance matrix are estimated by a mixed effects model repeated measure (MMRM) including the fixed categorical covariates of treatment, visit and the baseline ZAN-BPD total score strata indicator ( $\leq 18$  vs.  $\geq 19$ ), the continuous fixed covariate of baseline ZAN-BPD total score, and treatment-by-visit interaction, as well as baseline-by-visit interaction. Patient is considered as random. The unstructured covariance matrix is used to estimate the within subject variability. The Kenward-Roger approximation will be used to estimate the denominator degrees of freedom. Analyses will be implemented using SAS 9.4 PROC MIXED.

More specifically, the change in ZAN-BPD from baseline (Visit 2), at Visits 3, 4, 5, 6, 7 and 8 (Weeks 1, 2, 4, 6, 8 and 10) will be evaluated using an MMRM accounting for the following sources of variation: 'treatment', 'visit', 'baseline ZAN-BPD strata indicator' ( $\leq 18$  vs.  $\geq 19$ ),

‘baseline ZAN-BPD’ as a continuous covariate, and the ‘treatment\*visit’ and ‘baseline\*visit’ interaction as fixed effects, as well as the random ‘subject’ effect. The methods described in [Section 10.1](#) will be utilized to resolve model non-convergence.

SAS code for MMRM:

The following SAS code will be used to calculate the MMRM.

```
PROC MIXED DATA=indata cl method=reml;
    CLASS visit trt stratum subject;
    MODEL ept = stratum visit*trt base*visit / ddfm=kr s CL;
    REPEATED visit / subject= subject type=un r rcorr;
    LSMEANS visit*trt / pdiff=all om cl alpha=0.10 slice=visit;
```

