#### 3.3.2 Inclusion criteria

1. Patients meeting diagnostic criteria of BoPD per DSM-5 at screening visit, confirmed by SCID-5-PD.
2. ZAN-BPD of  $\geq 9$  at screening (Visit 1) and randomization (Visit 2), with question #2 Affective Instability score of  $\geq 2$ .
3. Male or female patients, 18-65 years of age at the time of consent

4. Women of childbearing potential (WOCBP) able and willing to use two methods of contraception, as confirmed by the investigator, which include one highly effective method of birth control per ICH M3 (R2) that results in a low failure rate of less than 1%, plus one barrier method (refer to section [4.2.2.3](#)).
5. Signed and dated written informed consent in accordance with ICH-GCP and local legislation prior to admission to the trial.

[REDACTED]

[REDACTED]

[REDACTED]

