The primary treatment comparisons will be the contrasts between each BI 1358894 treatment arm and placebo at Week 10. Procedures to be followed if the planned analysis fails to converge will be described in the TSAP. Resulting adjusted estimates from the MMRM will then be extracted for use in the MCPMod analysis. Parameter estimation of the MMRM will be based on the residual maximum likelihood method (REML).

For the PoC testing and for the sample size calculations, the basic shape of each of the models to be tested must be predefined. The candidate models in Table 7.2.2.1: 1 were selected to cover a plausible and diverse range of dose response patterns for the trial medication. Associated graphs of each model are shown in Figure [7.2.2.1: 1](#).

Table 7.2.2.1: 1 Models for the MCPMod analysis

Model	Estimate	Rationale
E max 1	50% of the maximum effect is achieved at 25 mg	E max curve corresponds the assumed true estimate of ED 50 =25 mg.
E max 2	70% of the maximum effect is achieved at 5 mg	To cover the possibility for which 70% of the maximum effect is achieved at 5 mg. This is a scenario in which much of the effect is achieved early on with relatively low doses. The rationale behind the two E max models is to construct one (e max 1) where the dose response is achieved as expected, while the other (e max 2) accounts for the setting of which the assumed dose response is not as expected.
Sigmax	50% of the maximum effect is achieved at 25 mg, and 90% of the maximum effect is achieved at 75 mg	Another more flexible model to cover the new estimate ED 50 =25 mg
Exponential	5% of the maximum effect is achieved at 25 mg	To cover the case where the effect of drug is mainly achieved at the higher doses.
Linear	No parameter assumptions required	In the event, dose response is linear.

The models were based on the following assumptions:

- BI 1358894 dose groups 5mg, 25mg, 75mg, 125mg and
- ED50 = 25 mg \*

\* ED50 assumes dose corresponding to EC50, FST = 77nM plasma concentration in trough at 16h.

EC50: Half maximal effective concentration

EC50 of a graded dose response curve represents the concentration of a compound where 50% of its maximal effect is observed.

FST: forced swim test (in mice)

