#### 7.5 DETERMINATION OF SAMPLE SIZE

Sample size is estimated assuming a maximum standardized effect size of 0.32, which is based on a mean difference between placebo and BI 1358894 of 3.0 and standard deviation of 9.5 for the primary endpoint, a one-sided alpha of 0.10, a treatment allocation ratio of 2.5:1:1:1:2 (placebo, BI 5mg, BI 25mg, BI 75mg, BI 125mg, respectively) and the pre-specified models listed in section [7.2.2.1](#). Information on the change from baseline and its standard deviation is limited since there is no BoPD approved drug. BoPD is a symptomatic and clinically heterogeneous condition and in clinical studies a high discontinuation rate has been observed. Consequently, sample size assumptions are based on expert opinion, previous BoPD research and a quetiapine pivotal trial ([R19-1108](#), [R19-1645](#), [P11-04859](#)).

For the PoC analysis of the BI 1358894 dose groups and placebo using MCPMod approach with the parameters as listed in section [7.2.2](#), a sample size of 285 (95:38:38:38:76) evaluable patients are needed to establish PoC with about 81% average power (one-sided 10% alpha level). The powers for each model shape under different assumptions are summarized in the table below.

Assuming a 20% dropout rate is considered reasonable based on unique characteristics of this population. Therefore, a total sample size of approximately 355 randomized patients are needed for this phase II trial:

- 119 patients in placebo arm
- 47 patients in each of the three lowest BI 1358894 arms
- 95 patients in the highest BI 1358894 arm

The calculations for the PoC step have been performed using DoseFinding R-package ([R15-2001](#)). The R codes for the sample size calculations as well as the analyses using the MCPMod approach will be provided in the TSAP. The family-wise type I error rate at one sided  $\alpha = 10\%$  is controlled in the sample size calculations and the analyses.

Table 7.5: 1 Power of MCPMod for each candidate set model and average power for change from baseline in ZAN-BPD at Week 10

Model	Assumption A	Assumption B	Assumption C
Maximum effect size	0.32 (Mean=3, SD=9.5)	0.35 (Mean=3.3, SD=9.5)	0.38 (Mean=3.6, SD=9.5)
Linear	81.9%	86.7%	91.6%
E max 1	81.7%	87.7%	91.6%
E max 2	75.2%	82.7%	86.6%
Sigmax	85.4%	89.1%	93.7%
Exponential	81.0%	85.8%	90.5%
Average	81.1%	86.4%	90.8%

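### The primary MMRM adjusts for the Visit 2 ZAN-BPD score but not the Visit 1 score that every eligible patient also has; this is valid, but leaves a free and probably modest precision gain unused

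*SAP*

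**What the plan says.** Inclusion criterion 2 (Protocol 3.3.2) asks for a ZAN-BPD total of 9 or more "at screening (Visit 1) and randomization (Visit 2), with question #2 Affective Instability score of" 2 or more. The screening rating is audio-recorded and reviewed externally for eligibility (Protocol 6.2.1, Eligibility Review). Every eligible randomized patient therefore has two pre-treatment scores.

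The primary model (SAP 7.4.1, MMRM analysis) contains treatment, visit, the stratum indicator, "the continuous fixed covariate of baseline ZAN-BPD total score, and treatment-by-visit interaction, as well as baseline-by-visit interaction". The printed SAS model has stratum, visit-by-treatment and baseline-by-visit terms, and nothing from Visit 1. The stratum is the baseline total cut at 18/19, so both severity terms carry one rating. The role given to Visit 1 is this: "if data at Visit 2 is missing, then data from Visit 1 will be considered baseline".

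The sensitivity model with additional risk factors (SAP 7.4.2.1) adds psychotherapy and sex, but not the Visit 1 score. Protocol 7.2.2.1 leaves room for further covariates identified before database lock. The Flow Chart also schedules DERS-16, STAI-S and PHQ-9 at Visits 1 and 2, and SAP 7.5.2 analyses them with a model like the primary one. CGI-S and PGI-S are not scheduled at Visit 1.

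**The concern.** ZAN-BPD is an interview rating with a one-week recall (Protocol 5.1), and Visit 2 falls 7 to 28 days after Visit 1 (Flow Chart). One rating is a noisy reading of a patient's usual severity, above all in a disorder marked by affective instability. A second rating from a different week would normally explain some further Week 10 variance.

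The adjusted means and covariance matrix from this model feed both the proof-of-concept test and the fitted dose-response curve. Any avoidable residual variance therefore reaches the test and the target-dose estimate. The stake is efficiency: neither bias nor type I error is in question.

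**Working it through.** **Inputs from Protocol 7.5 and 7.2.2.1.** The design assumes a "mean difference between placebo and BI 1358894 of 3.0 and standard deviation of 9.5 for the primary endpoint, a one-sided alpha of 0.10", and states that "a sample size of 285 (95:38:38:38:76) evaluable patients are needed to establish PoC with about 81% average power". The candidate shapes are linear; Emax with ED50 25 mg; Emax with 70% of the maximum effect at 5 mg (ED50 2.14 mg); sigmoid Emax (ED50 25 mg, Hill coefficient 2); and exponential with 5% of the maximum effect at 25 mg (delta 45.4).

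**Step 1: reproduce the plan.** Optimal contrasts weighted by arm size reproduce all 25 coefficients in SAP Table 7.4.1:1 to three decimals. The simulated maximum-contrast test (280 df, critical value about 1.62) gives average power of 81.4%, against 81.1% stated. For Assumptions B and C it gives 86.7% and 90.9%, against 86.4% and 90.8%. With 20% dropout, 285/0.8 = 356.25, consistent with about 355. Two single-shape powers in Table 7.5:1 do not reproduce (Emax 2: 75.2% stated, 81.9% computed; exponential: 81.0% stated, 78.8% computed), so only averages are used below.

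**Step 2: variance formula.** Let r1 and r2 be the correlations of Visit 1 and Visit 2 with Week 10, and r12 the correlation between Visits 1 and 2.

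- R² with both scores = (r1² + r2² − 2·r1·r2·r12) / (1 − r12²)
- Variance ratio = (1 − R²) / (1 − r2²)
- Equivalent extra evaluable patients = 285/ratio − 285

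Best case in the grid, (0.5, 0.5, 0.5): R² = (0.25 + 0.25 − 0.25)/0.75 = 0.333; ratio = 0.667/0.75 = 0.889.

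Visit 1 weaker, (0.4, 0.5, 0.7): R² = (0.16 + 0.25 − 0.28)/0.51 = 0.255; ratio = 0.745/0.75 = 0.993.

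AR(1) decay, (0.35, 0.5, 0.7): R² = (0.1225 + 0.25 − 0.245)/0.51 = 0.25; ratio = 1.000.

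**Step 3: power.** The SD becomes 9.5·√ratio, with contrasts and arm sizes held fixed. This takes 9.5 as the SD after Visit 2 adjustment. All correlations are assumptions. Repeat simulations differ by 0.1 to 0.2 points.

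| r1, r2, r12 | Ratio | Variance cut | Extra patients | Average power |
|---|---|---|---|---|
| none added | 1 | – | – | 81.4% |
| 0.50, 0.50, 0.50 | 0.889 | 11.1% | 36 | 84.8% |
| 0.45, 0.50, 0.60 | 0.953 | 4.7% | 14 | 82.7% |
| 0.45, 0.50, 0.70 | 0.974 | 2.6% | 8 | 82.0% |
| 0.40, 0.50, 0.70 | 0.993 | 0.7% | 2 | 81.5% |
| 0.35, 0.50, 0.70 | 1.000 | 0% | 0 | 81.4% |

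With both visits equally predictive but weaker, (0.4, 0.4, 0.7), the cut is 3.4%, or about 10 patients.

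**Step 4: is zero gain typical?** Exact AR(1) in the observed scores implies ratings without measurement error. Suppose instead that true severity follows AR(1) and each rating has reliability ρ. With true-severity correlation a between Visits 1 and 2, and b from Visit 2 to Week 10, r1 = ρab, r2 = ρb and r12 = ρa. Taking ρ = 0.6 to 0.8, a = 0.85 to 0.95 and b = 0.6 to 0.8 (all assumed), the cut is about 2 to 6%, or roughly 5 to 20 patients.

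**The case against.** The strongest reply is that this is a preference, since adjustment for baseline, its visit interaction and the stratum is a complete specification. That stands: no document requires a second pre-treatment score, and the planned power never relied on one.

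The size can also be challenged, and these points stand too:

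- Cuts of 5 to 11% need Visit 1 to predict Week 10 about as well as Visit 2. Visit 1 is older, by up to 28 days, and psychotropic drugs may be washed out in between (exclusion criterion 6), so some Visit 1 ratings come from a different treatment state.
- Protocol 7.5 gives 9.5 as the SD of the primary endpoint without saying whether it is before or after baseline adjustment. If it is the raw SD of change (equal variances and r = 0.5 assumed), its variance is 2(1 − 0.5)σ² = σ². The residual after Visit 2 adjustment is (1 − 0.25)σ² = 0.75σ², the SD falls to 8.23, and average power is already about 89%. Visit 1 then adds at most about 3 points.

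Three stronger readings are tempting. A reader might infer that the trial is underpowered because Visit 1 is left out; the stated average power reproduces without it, so no shortfall is shown. A reader might say the score is discarded; it serves eligibility and is the fallback baseline. A reader might expect larger gains from higher correlations: three equal correlations of 0.7 would cut variance by 17% and raise average power to 86.7%. Nothing in the documents supports values that high out to Week 10.

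That the protocol already permits extra covariates does not answer the point. The SAP has used that room for psychotherapy and sex only, and only in a sensitivity analysis.

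**Conclusion.** The point holds as a missed efficiency in a valid analysis. Both scores exist by eligibility rule, and the primary model uses only one of them. The likely gain is a few percent of residual variance, within a range of about 0 to 11%: roughly 0 to 36 evaluable patients on 285, and about 0 to 3 points of average power if 9.5 is the SD after Visit 2 adjustment.

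The size rests entirely on assumed correlations of 0.35 to 0.5 with Week 10 and 0.5 to 0.7 between the two visits, with Visit 1 no more predictive than Visit 2. It could be negligible. The change is still worth making, because it uses data already collected and leaves the endpoint, the estimand and type I error control unchanged. SAP sections 6.4 and 10 are not in the public text, so a Visit 1 term there cannot be excluded; the printed primary code has none.

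**What to change.** Before unblinding, amend SAP 7.4.1:

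1. Add the Visit 1 ZAN-BPD total score as a second continuous covariate with its visit interaction: `MODEL ept = stratum visit*trt base*visit scr*visit`. Keep Visit 2 as the baseline that defines change.
2. Define `scr` as the last valid screening score from the screening episode that led to randomization. This is needed because Protocol 6.2.1 lets screening evaluations be repeated once and has rescreened patients repeat Visit 1.
3. Give a simple rule for a missing Visit 1 score, and for the case where Visit 1 itself serves as baseline (`scr` would then equal `base`). One option is to impute `scr` with the overall mean of the Visit 1 scores, blind to treatment. The second case should be rare, because ZAN-BPD must be completed before randomization (Flow Chart, note 12).
4. Do the same for DERS-16, STAI-S and PHQ-9 with their own Visit 1 scores. CGI-S and PGI-S stay as they are.

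The cost is a short SAP paragraph, one code term and six extra slopes, one for each of Weeks 1, 2, 4, 6, 8 and 10. There is no new data collection and no patient burden. The downside is that the gain may prove negligible.
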